### 4.2 Analysis Sets

The primary endpoint and additional measurements will be analyzed on an ITT and an implanted basis.

Among the randomized cohorts (the Main Randomized, the 4D-CT, and the Extended Durability Cohorts), for ITT analyses, all subjects who sign the IRB/REB/HREC/ IEC - approved study ICF, are enrolled in the trial, and are randomized will be included in the analysis, whether or not an assigned study valve (ACURATE or Control) was implanted. For Implanted analyses, ITT subjects who had the assigned (Test versus Control), randomized study valve implanted will be included in the analysis. For the implanted randomized cohort analysis set, if a subject receives 2 different valve types from 2 different manufacturers, the subject will be excluded from the implanted analysis.

With the roll-in cohort, the ACURATE *Prime* XL Nested Registry cohort, and the Continued Access Study, the subject is considered enrolled in the trial when there is an attempt made to insert the ACURATE Transfemoral Aortic Valve System into the subject's femoral artery. For ITT analyses, all subjects who sign the IRB/REB/HREC/ IEC -approved study ICF and are enrolled in the trial will be included in the analysis sample, regardless of whether the study device was implanted. The implanted population includes all subjects who sign an ICF and are implanted with an ACURATE valve.

For the randomized cohorts (the Main RCT, the 4D-CT, and the Extended Durability cohorts), the subjects will be analyzed for the ITT and implanted analysis sets. The primary analysis for the primary endpoint will be based on the ITT analysis set.

For ITT analysis set, events starting from the randomization date will be included in the analysis for the randomized cohorts (the Main RCT, the 4D-CT, and the Extended Durability cohorts) and events starting from the procedure date will be included in the analysis for the roll-in cohort, the ACURATE *Prime* XL Nested Registry cohort, and the Continued Access Study. For the Implanted analysis sets, events starting from the procedure date will be included in the analysis.

With the 4D CT cohort, the 4D CT imaging analysis is based on the implanted analysis set. 4D CT data will be pooled with available ACURATE neo2 PMCF data. The pooled data and individual 4D CT cohort will be analyzed.

The analysis set at the formal interim is the subset of randomized subjects who had completed 30-day, 6-month, and/or 1-year follow-up as defined in Section 3.1.5.1. The analysis set (N=1500) at the final will include all enrolled subjects.

## 4.3 Control of Systematic Error/Bias

All subjects who have met the inclusion/exclusion criteria, received a positive recommendation from the CRC, and signed the Informed Consent Form will be eligible for enrollment in the study. The center heart team's assessment of TTE measurements before device placement will contribute to the determination of subject eligibility for the study.

To control for inter-observer variability, data from independent core laboratories will be used for analysis. These include an echocardiography core laboratory and a CT/angiography core laboratory to assess all data using standard techniques. Clinical endpoints will also be adjudicated by an independent CEC.

The study team is blinded to aggregated data reports prior to the official study unblinding at the formal interim analysis.

## 4.4 Randomization Schedule

For the Main Randomized Cohort and Extended Durability Study, a computer-generated list of random treatment allocations for each cohort (i.e., a randomization schedule) will be used to assign subjects in the ACURATE IDE trial to treatment in a 1:1 ratio of ACURATE to Control. Randomization will be stratified by center and by intended control device (SAPIEN or CoreValve). Additional information is provided in the study Manual of Operations.

### 4.5 Number of Subjects per Investigative Site

Enrollments shall not exceed 18% of total enrolled RCT subjects at any individual investigative site for the ACURATE IDE study. There is no set minimum number of subjects to be enrolled per site. "Small sites" will be -removed for poolability analyses (see Section 5.5.1).

# 5 ADDITIONAL DATA ANALYSES

# 5.1 Adjudicated CEC Event Analysis

For clinical events, the cut-off for events for 30-day endpoints will be 30 days, for 6month endpoints it will be 180 days, for 1-year endpoints it will be 365 days, and for endpoints at 2–10 years it will be 365 days times the number of years. For events at discharge or 7 days post-procedure, the cut-off for events will be the earlier date of discharge or 7 days post-procedure for each subject. The number of evaluable subjects for the CEC event includes subjects who have CEC confirmed events or are in study at least 23, 150, or 335 days (defined as sufficient follow-up in Section 7.3.3) for 30-day, 6month, or 1-year outcome analysis, respectively. For analysis at 2-10 years, the sufficient follow-up is defined as "number of years times 365 minus 45". The number of evaluable subjects for the CEC event at discharge will include all subjects in the specific analysis set.

The Kaplan-Meier rates for all CEC Events will be provided in analyses at 30 days, 6month, and 1-10 years. The survival analysis (including accumulated event curve) for time-to-event endpoint will be provided for selected CEC events, and log-rank test pvalue and wilcoxon test p-value will be provided for comparing two survival curves.

Event to be analysed include the following:

- o Mortality: all-cause, cardiovascular, and non-cardiovascular
- Stroke: disabling and non-disabling
- Myocardial infarction (MI): periprocedural (≤72 hours post index procedure) and spontaneous (>72 hours post index procedure)
- Bleeding: life-threatening (or disabling) and major (through 5 years)
- Acute kidney injury (AKI; ≤7 days post index procedure): based on the AKIN System Stage 3 (including renal replacement therapy) or Stage 2
- Major vascular complications (through 5 years)
- Repeat procedure for valve-related dysfunction (surgical or interventional therapy)
- Hospitalization for valve-related symptoms or worsening congestive heart failure (NYHA class III or IV)
- New permanent pacemaker implantation resulting from new or worsened conduction disturbances
- New onset of atrial fibrillation or atrial flutter
- Coronary obstruction: periprocedural (≤72 hours post index procedure)
- Ventricular septal perforation: periprocedural ( $\leq$ 72 hours post index procedure)
- Mitral apparatus damage: periprocedural ( $\leq$ 72 hours post index procedure)
- Cardiac tamponade: periprocedural (≤72 hours post index procedure)
- Valve migration
- Valve embolization
- Ectopic valve deployment
- Transcatheter aortic valve (TAV)-in-TAV deployment
- Prosthetic aortic valve thrombosis
- Prosthetic aortic valve endocarditis

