#### 3.1.5 Interim Analysis

#### 3.1.5.1 Completed visits at 30-day, 6-month, and 1-year

The interim analysis for the primary endpoint will be conducted after 1050 subjects in the Main Randomized Cohort have completed a 1-year follow-up, or at least 80% low risk subjects in the Main Randomized Cohort have completed a 6-month follow-up, whichever comes later. A subject is considered as completion of 1-year follow-up if the subject meets the following by the pre-specified cutoff date (defined in 3.1.5.2):

- 1) has completed 1-year follow-up visit, or
- 2) has not completed 1-year follow-up visit and is reported in the 1-year visit form as 'not done' or in the End-of-Study form (as died, withdrew, or lost to 1-year follow-up) and has reached 365 days post index procedure (or randomization if no procedure), or
- 3) has not completed 1-year follow-up visit and is not reported as 'not done' or not in the End-of-Study (as died, withdrew, or lost to 1-year follow-up) and has reached 395 days post index procedure (or randomization if no procedure).

Similarly, a subject is considered as completed 30-day and 6-month follow-up visits as the following:

For 30-day visit by the pre-specified cutoff date (defined in 3.1.5.2):

- 1) has completed 30-day follow-up visit, or
- 2) has not completed 30-day follow-up visit and is reported in the 30-day visit form as 'not done' or in the End-of-Study form (as died, withdrew, or lost to 30-day follow-up) and has reached 30 days post index procedure (or randomization if no procedure), or
- 3) has not completed 30-day follow-up visit and is not reported as 'not done' or not in the End-of-Study (as died, withdrew, or lost to 30-day follow-up) and has reached 37 days post index procedure (or randomization if no procedure).

For 6-month visit by the pre-specified cutoff date (defined in 3.1.5.2):

- 1) has completed 6-month follow-up visit, or
- has not completed 6-month follow-up visit and is reported in the 6-month visit form as 'not done' or in the End-of-Study form (as died, withdrew, or lost to 6month follow-up) and has reached 180 days post index procedure (or randomization if no procedure), or
- 3) has not completed 6-month follow-up visit and is not reported as 'not done' or not in the End-of-Study (as died, withdrew, or lost to 6-month follow-up) and has reached 210 days post index procedure (or randomization if no procedure).

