# 3.4 Other Endpoints

Additional analyses at interim for other CEC endpoints will be performed on all enrolled Main Randomized Cohort subjects (N=1500) using the piecewise exponential prediction models specified in Section 3.1.5. Event rates and credible intervals will be provided.

For the Main Randomized Cohort (including 4D-CT Cohort subjects), the 4D-CT Cohort, and the Extended Durability Study, the analysis will be conducted separately. Statistical comparisons for these endpoints will be made between the test and the control arms within each cohort. 4D-CT analysis will include the data for subjects who are eligible for the Main Randomized Cohort analysis at the time of the interim analysis. Analyses for other endpoints will use the standard frequentist methods (details in Section 4.1), such as Chi-square or Fisher's exact for binary variables, T-test for continuous variables, or Log-rank test for time-to-event or Kaplan–Meier survival analysis when they are appropriate, at both the interim and the final analyses. Additional analysis methods may be used when they are appropriated (e.g. Breslow-day test for interaction, ANOVA test or Kruskal-Wallis test for continuous variables, one-sample T-test or McNemar's test for paired analysis).

For the roll-in, the ACURATE *Prime* XL Nested Registry, and the Continued Access Study cohorts, the analyses will be conducted separately, and descriptive analyses will be provided.

Reference:

FDA Guidance for Industry and FDA Staff: Guidance for the Use of Bayesian Statistics in Medical Device Clinical Trials, February 2010

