#### 7.3.3 Event Rates

The calculation of binary rates will be the same for any endpoint and time point in regard to the appropriate numbers of days as indicated below in Table 1

Table 1. Days Post-procedure to Event and for Adequate Follow-up for ITT and
Implanted Analysis Sets.

Follow-up Visit	Maximum Days to Event	Days for Adequate Follow-up	
	from	from	
	Randomization/Procedure*	Randomization/Procedure**	
30 Days	30	23	
6 Months	180	150	
12 Months	365	335	
2 Years	730	685	
3 Years	1095	1050	
4 Years	1460	1415	
5 Years	1825	1780	
6 Years	2190	2130	
7 Years	2555	2495	
8 Years	2920	2860	
9 Years	3285	3225	
10 Years	3650	3590	

\* Target date for the follow-up visit.

\*\* Start of the follow-up visit window.

Note: For ITT analysis, the Days are from randomization date. For Implanted, the Days are from procedure date (for non-RCT cohorts, the Days are from procedure date).

Binary event rates (proportions) are calculated on a per subject basis.

Event rates through a follow-up visit are calculated using the following for inclusion in the denominator and numerator:

• Denominator:

Subjects in the specific analysis set count in the denominator with one of the following:

- Subject experiences any CEC adjudicated event ≤ maximum number of days as specified in Table 1, as appropriate or
- $\circ$  date of last follow-up  $\geq$  days for adequate follow-up post-procedure from Table 1, as appropriate:
- Numerator:

Subjects in the specific analysis set count in the numerator if the subject experiences specified event  $\leq$  maximum number of days as specified in Table 1, as appropriate.

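### At the formal interim, crude 6-month and 1-year clinical-event proportions and their tests use a denominator that depends on outcome

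*SAP*

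**What the plan says.** Five parts of the SAP bear on this.

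- **Evaluable subjects (5.1).** The evaluable number for a clinical event "includes subjects who have CEC confirmed events or are in study at least 23, 150, or 335 days". The cut-off for counting events is longer than the minimum follow-up: "for 1-year endpoints it will be 365 days".
- **Event rates (7.3.3).** "Subjects in the specific analysis set count in the denominator with one of the following": either "Subject experiences any CEC adjudicated event ≤ maximum number of days as specified in Table 1", or last follow-up at or beyond the start of the visit window (335 days for 1 year). The event route is any adjudicated event, not only the one being tabulated.
- **Analysis set (4.2).** "The analysis set at the formal interim is the subset of randomized subjects who had completed 30-day, 6-month, and/or 1-year follow-up". This is a union of the three groups.
- **Methods (3.4).** Interim rates for the other adjudicated endpoints come from the piecewise exponential models. The section then plans standard frequentist methods for other endpoints, including chi-square and Fisher tests, "at both the interim and the final analyses". Section 5.1 adds Kaplan-Meier rates for all adjudicated events.
- **Cohorts (3.1.5.1 and 3.1.5.2).** Separate 30-day, 6-month and 1-year cohorts are defined and assigned to the three intervals of the piecewise models. A subject who died, withdrew or was lost counts as a 1-year completer only if recorded as "lost to 1-year follow-up) and has reached 365 days post index procedure" (or randomization, if there was no procedure).

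**The concern.** When every subject has had the chance to reach 1 year, the rule in 5.1 and 7.3.3 does little harm. It drops a few early withdrawals without events. At the interim, many subjects are short of 335 days only because they were enrolled recently. Among them, those with an event are counted and those without are left out, so the denominator is selected on outcome. The 6-month tables have the same fault on a smaller scale.

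The SAP guards against this where the primary endpoint is concerned: the 1-year cohort waits for 365 days to elapse even for subjects who have died. Its revision history gives avoidance of selection bias as the reason for defining the interim cohorts. Nothing carries that guard over to the binary tables.

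If non-inferiority is declared at the interim, that test is not repeated at the final analysis. The interim safety tables may then be read closely. A crude proportion several points above the Kaplan-Meier rate for the same event would need explaining, and its p-value would rest on a selected denominator.

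**Working it through.** The SAP gives no figure for this rule, so the check starts from its interim assumptions.

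**Follow-up at the interim (SAP Table 2, per arm).**
- 30-day: 262 + 225 + 262 = 749
- 6-month: 241 + 225 + 223 = 689
- 1-year: 194 + 221 + 115 = 530. Two arms give 1060, in line with the 1050 that trigger the interim.
- Short of 1 year: 749 - 530 = 219, of whom 689 - 530 = 159 have passed 6 months and 749 - 689 = 60 have passed only 30 days.

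**Event curve.** Take the SAP's 22.3% at 1 year as an illustrative rate, with the hazard pattern the SAP calls expected (second interval 0.3 and third 0.2 times the first).
- h = -ln(1 - 0.223) / (30 + 0.3×150 + 0.2×185) = 0.2523/112 = 0.002253 per day
- F(30) = 1 - exp(-30h) = 6.5%
- F(180) = 1 - exp(-75h) = 15.5%

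**Crude 1-year proportion if only the analysed event admits.** Rate = (530×0.223 + E)/(530 + E), where E is the number of events among the 219.
- Follow-up at the last completed visit: E = 159×0.1555 + 60×0.0654 = 28.6, so (118.2 + 28.6)/558.6 = 26.3%. Over the four hazard cases of SAP Table 3: 25.9-27.0%.
- Follow-up spread evenly (180-335 and 30-180 days; mean F 18.4% and 11.1%): E = 29.3 + 6.7 = 36.0, so 154.2/566.0 = 27.2%. Over the four cases: 27.0-27.7%.

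**Crude 1-year proportion if any adjudicated event admits (7.3.3 as written).** Add to the denominator a share a of the 219 - 36 = 183 recent subjects without the analysed event. The documents do not give a, so it is assumed. With follow-up spread evenly, rate = 154.2/(566.0 + 183a):
- a = 20%: 25.6%
- a = 30%: 24.8%
- a = 40%: 24.1%

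The bias is zero when the admitted recent subjects number E/0.223. That is 28.6/0.223 = 128 (59% of 219) with follow-up at the last visit, or 36.0/0.223 = 161 (74%) with follow-up spread evenly. Beyond that it turns negative.

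**Other event rates.** Four rows of SAP Table 4 were tried (CoreValve high and intermediate risk, and the two low-risk studies), with follow-up at the last visit. The relative change in the crude 1-year rate was:
- only the analysed event admits: +20% to +26%
- any-event incidence 30% at 30 days and 40% at 6 months (assumed): +6% to +11%
- 45% and 55%: +1% to +6%
- 50% and 70%: -3% to +2%

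**6-month table.** With the same curve, analysed-event admission and last-visit follow-up: (689×0.1555 + 60×0.0654)/(689 + 60×0.0654) = 111.0/692.9 = 16.0%, against a true 15.5%.

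**Comparison of estimators.** In a simulation of 4000 interim data sets with follow-up spread evenly and a true rate of 22.3%, the crude rule averaged 27.2%. Kaplan-Meier, the piecewise model and the crude rate restricted to the 1-year cohort each averaged 22.3%.

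**The case against.** The strongest reply is that SAP 3.4 opens by giving the interim rates for adjudicated events to the piecewise models, and 5.1 supplies Kaplan-Meier rates for all of them. Both handle incomplete follow-up, so only a supplementary crude proportion is exposed. This stands, and it limits the point to the binary tables and their tests. It does not repair them: 3.4 still plans those tests at the interim, and 7.3.3 sets one calculation for all binary rates.

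Second, the analysis set meant in 7.3.3 could be the completers of the matching visit, in which case the bias disappears. That reading is possible, but 4.2 defines the interim set as the union and 3.1.5.2 ties the visit cohorts to the models. The text as written leads to the selected denominator.

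Third, admission on any adjudicated event brings in subjects without the event being analysed. This stands: it makes the 26-27% an upper bound and leaves the direction open in extreme cases. It also means that the denominator for one endpoint depends on unrelated events. If those differ by arm, equal true rates can look unequal. With 20% against 40% of other recent subjects admitted (assumed), a common 22.3% would show as 25.6% and 24.1%.

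Fourth, Protocol 11.1.4 plans no inferences on these measurements, and the rule is the same in both arms. That stands as a limit on the consequences. With equal event rates and equal admission, no false difference arises.

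**Conclusion.** The point holds for the crude 6-month and 1-year proportions at the formal interim and for the chi-square or Fisher tests on them. As written, 4.2, 5.1 and 7.3.3 together select the denominator on outcome. The bias is usually upward. For an illustrative true 22.3% at 1 year it is at most about 4 to 5 points, falls to roughly 2 to 3 points if 20-30% of the other recent subjects enter through another event, and can vanish or slightly reverse at very high any-event incidence. At 6 months it is about half a point on the case worked. These sizes rest on the Table 2 counts, the SAP's hazard patterns and assumed any-event incidences.

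A reader might infer that all interim 1-year event rates are inflated, that the inflation is always upward, or that the non-inferiority result is at risk. The documents support none of these. The model-based rates (3.4) and Kaplan-Meier rates (5.1) do not use the rule. Admission on any adjudicated event can offset the bias. The primary test uses posterior sampling from the piecewise models (3.1.5.3 and 3.1.5.4), and the 22.3% serves here only as an example rate.

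**What to change.** In SAP 4.2, 5.1 and 7.3.3, state that at the formal interim the 30-day, 6-month and 1-year binary tables and tests use only the matching analysis cohort of SAP 3.1.5.2, for numerator and denominator alike. State also that results on all enrolled subjects are reported as Kaplan-Meier or model-based rates, which the SAP already plans. Make the change before the interim unblinding.

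The cost is one sentence and a cohort filter in the programs. The interim crude tables will have slightly fewer subjects. On Table 2, the 1-year tables rest on 530 per arm, without the recent subjects admitted through events.

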10.10.4. Annual Follow-up (±45 Days) to 5 Years

All implanted subjects must be evaluated in person or by telehealth visit at 2, 3, 4, and 5 years after the index procedure, with a window of ±45 days. During the annual follow-up, the following assessments must be completed. The ACURATE IDE eCRFs identify the specific data points to be collected.

- Weight
- NYHA classification
- Modified Rankin Scale score, which must be performed by a neurology professional or certified personnel (external or internal certification); mRS assessors should be independent (not involved with the care of study subjects).
- Current antiplatelet, anticoagulant (if applicable)
- TTE, including assessment of EOA, peak and mean aortic valve gradient pressure, aortic regurgitation assessment, mitral regurgitation, LVEF, left ventricular enddiastolic and end-systolic diameter, TR jet velocity, and LA volume, per the Echocardiography Core Laboratory procedure guidelines. All TTEs must be forwarded to the core laboratory for independent analyses.

Note: TTE must be done for all subjects who have a transcatheter valve implanted in the aortic position during the index procedure, even if the associated follow-up assessment is carried out via telehealth. Subjects who do not receive a transcatheter valve during the index procedure are not required to have follow-up TTE.

- Complete serious adverse event (SAE, SADE, UADE, and CEC events) assessment for test and control devices and device deficiencies assessment for test device(s) with associated treatment.
- Quality of Life Surveys: Kansas City Cardiomyopathy and SF-12 Quality of Life Questionnaires at 5 years

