10.10.6. Follow-up (±60 Days) at 6, 8 and 9 Years

All implanted subjects must be evaluated at 6, 8, and 9 years after the index procedure, with a window of ± 60 days. This evaluation may be conducted by telephone. The following assessments must be completed. The ACURATE IDE eCRFs identify the specific data points to be collected.

- Current antiplatelet, anticoagulant (if applicable)
- Serious adverse event (SAE, SADE, UADE, and relevant VARC events to be adjudicated by the CEC) assessment for test and control devices and device deficiencies assessment for test device(s) with associated treatment. Please see Section 10.10.5 for a list of relevant VARC events.

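### SAP 5.1 and SAP 7.3.3 set sufficient follow-up at years 6-10 fifteen days apart, so the same binary CEC event rates have two denominators; the effect is probably small and falls mainly on year 10

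*SAP*

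**What the plan says.** SAP 5.1 makes a subject evaluable for a binary event rate by either of two routes, a confirmed event or enough time on study: "The number of evaluable subjects for the CEC event includes subjects who have CEC confirmed events or are in study at least 23, 150, or". The list closes with a third value, 335, and the three serve the 30-day, 6-month and 1-year analyses in turn. It refers to SAP 7.3.3 for those three values. For every analysis from year 2 to year 10 it then gives a single formula, "number of years times 365 minus 45".

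Table 1 of SAP 7.3.3 lists the thresholds one by one. The year 5 row reads "5 Years 1825 1780", which is 45 days before target. The year 6 row reads "6 Years 2190 2130", which is 60 days before target, and years 7-10 follow the same pattern. The footnote explains the threshold as "Start of the follow-up visit window".

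The protocol windows change at the same point. Section 10.10.4 is titled "Annual Follow-up (±45 Days) to 5 Years". Section 10.10.5 sets ±60 days for years 7 and 10. Section 10.10.6 requires subjects to be "evaluated at 6, 8, and 9 years after the index procedure, with a window of" ±60 days.

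**The concern.** Both SAP sections are current text and both define who counts in the denominator of the same tables. Two programmers, one working from 5.1 and one from 7.3.3, would produce different denominators at years 6-10. If the conflict surfaced only when the tables were built, the choice between them would be made with data in hand.

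The difference has a direction. Subjects with a CEC event stay in the denominator however short their follow-up, so a stricter follow-up requirement can remove only subjects without one. At years 6-10 the 5.1 rule would set aside some event-free subjects last seen inside the permitted visit window, and the reported binary rate would rise.

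**Working it through.** **Thresholds.** The inputs are the Table 1 values (SAP 7.3.3), the 5.1 formula and the protocol half-windows (sections 10.10.4 to 10.10.6). The target is 365 × years.

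| Year | Target | Table 1 | Target minus Table 1 | Protocol half-window | SAP 5.1 (target minus 45) | 5.1 minus Table 1 |
|---|---|---|---|---|---|---|
| 2 | 730 | 685 | 45 | 45 | 685 | 0 |
| 3 | 1095 | 1050 | 45 | 45 | 1050 | 0 |
| 4 | 1460 | 1415 | 45 | 45 | 1415 | 0 |
| 5 | 1825 | 1780 | 45 | 45 | 1780 | 0 |
| 6 | 2190 | 2130 | 60 | 60 | 2145 | 15 |
| 7 | 2555 | 2495 | 60 | 60 | 2510 | 15 |
| 8 | 2920 | 2860 | 60 | 60 | 2875 | 15 |
| 9 | 3285 | 3225 | 60 | 60 | 3240 | 15 |
| 10 | 3650 | 3590 | 60 | 60 | 3605 | 15 |

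Table 1 reproduces exactly as target minus the protocol half-window. This includes the early visits: 30 − 7 = 23, 180 − 30 = 150, 365 − 30 = 335. SAP 5.1 matches through year 5 and departs from year 6.

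**Who changes status.** These are subjects with no CEC event whose last follow-up falls from target − 60 to target − 46: days 2130-2144 at year 6, and on to days 3590-3604 at year 10. SAP 7.3.2 takes last follow-up as the latest of several dates (adverse events, admissions and discharges, visits, CEC events), so what matters is the last recorded contact.

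**Size.** The documents give no visit-timing data or expected 10-year rates, so what follows is assumption. Let r be the rate under Table 1, q the proportion kept because of an event (at least r), and s the share of the rest whose last contact lies in the 15-day band. Then

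rate under 5.1 = r / (1 − (1 − q) × s).

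Take r = 40% at year 10, counting days from the procedure.

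- Visits spread evenly over the 121-day window, q = r: s = 15/121 = 12.4%, and 0.40 / (1 − 0.60 × 0.124) = 43.2%.
- Visits centred on target within the window, SD 30 days: s = 4.6%, and 0.40 / (1 − 0.60 × 0.046) = 41.1%.
- The same with SD 20 days: s = 1.1%, and 0.40 / (1 − 0.60 × 0.011) = 40.3%.
- Even spread, but 70% of subjects have some CEC event by year 10: 0.40 / (1 − 0.30 × 0.124) = 41.5%.

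**ITT clock.** SAP 7.3.3 counts ITT days from randomization, while protocol section 10.1 times visits from the procedure, which should follow within 14 days (section 7.2). With a gap of g days, a visit d days early falls on ITT day target − d + g, so 5.1 excludes it only if d is above 45 + g. That leaves 15 − g affected days inside the window: 15 at g = 0, 8 at g = 7, 1 at g = 14. At g = 7 with even spread, 0.40 / (1 − 0.60 × 8/121) = 41.7%. The other g days of the ITT band lie just before the window opens, so an ITT subject in the band is not always an in-window attender.

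**The case against.** The strongest case on the other side accepts the conflict and disputes its reach. Four parts of it stand.

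- A reader might infer that every event-free subject who attends 46-60 days early at any of years 6-10 is lost. The documents do not support that. Neither rule tests the timing of a single visit, and under SAP 7.3.2 a subject seen early at year 6 and contacted at any later date counts under both rules. At years 6-9 the loss is confined to subjects with no later contact on record, such as dropouts or those caught by an early data cut. Year 10 is different because protocol section 10.11 ends participation at that visit.
- A reader might take 43.2% as the expected distortion. It needs even visit timing, a 40% rate, a procedure-based clock and only the analysed event counting for retention. SAP 7.3.3 keeps any subject with any adjudicated event, which shrinks the pool that can be dropped.
- SAP 7.3.3 says binary rates are computed the same way for any endpoint and time point using Table 1, and 5.1 points to 7.3.3 for its earlier thresholds. A careful programmer could reasonably settle on Table 1. SAP 5.1 also provides Kaplan-Meier rates for all CEC events through year 10, and those do not use the threshold.
- The rule applies to both arms, and protocol section 11.1.4 plans no inference on the additional measurements. A reader might also see these as the years the trial was extended to study durability, but the protocol's revision history records the 10-year extension only as a regulator's request.

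None of this removes the inconsistency or reverses its direction. The formula in 5.1 covers years 6-10 in so many words, and the subjects it newly excludes have no CEC event.

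**Conclusion.** The point holds as an internal inconsistency with a one-sided but probably small effect. The 15-day gap at each of years 6-10 is exact and needs no assumption. Table 1 is the version that agrees with the protocol windows and with its own footnote, so 5.1 is the text to change. Binary rates under 5.1 are equal to or higher than those under Table 1.

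The size rests on assumed visit timing and event rates. For a 40% year-10 rate counted from the procedure, the range worked here is 0.3 to 3.2 percentage points, and the top is an upper illustration. It applies most directly to year 10 in the Implanted set and the non-randomized cohorts. In ITT analyses the gap between randomization and procedure shrinks the in-window loss. The documents do not support a claim that the trial's main conclusion is at risk: the 1-year primary endpoint, years 2-5 and all Kaplan-Meier rates are unaffected.

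**What to change.** In SAP 5.1, replace the single formula for years 2-10 with a reference to Table 1 of SAP 7.3.3. Alternatively, state it in two parts: years 2-5, years × 365 minus 45; years 6-10, years × 365 minus 60. The reference is preferable because it leaves one definition to maintain.

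The cost is one line of SAP text. Data collection, sample size and the primary analysis do not change, and SAP 5.8 already provides for amending the plan before an analysis is performed.
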